During the weekly contact with the participant, the study staff will inquire about the frequency of walking and the availability of the companion. If the companion has not been able to walk with the participant in a past week, the study staff will try to resolve the problems. Additional companions will be suggested. Availability of the EAW companion(s) is an important consideration and a close eye on this process will be necessary. Since these exoskeletal devices are going to require walking companions as per the FDA, it will be important to know the feasibility of our Veterans and military members with SCI to have viable walking companions for use of an exoskeleton in the home/community environment. The number of eligible companions and the actual amount of walking time that the companions are available for the participants during the home-use phase can be determined in the Feasibility component of the study. If the companion requirement proves to be an obstacle during the feasibility, it can be addressed with each case and solutions can be made available for all study participants. If a companion is lost or withdraws from the study, then the participant will be obligated to re-train another companion, or the participant will be terminated from the study, an outcome that will be strenuously avoided. Of note, as a consequence of this clinical trial, it will also be determined if identifying a companion is a major obstacle to the use of the exoskeleton in our Veteran or military member population with SCI because, as previously stated, these devices cannot be prescribed for home use without a companion in attendance when this device is being used.

H. EAW Advanced Skills Test

The EAW Advanced Skills are in addition to the EAW Basic Skills. The EAW Advanced Skills Test will be passed by the participant and their companion(s) prior to being sent home with an

exoskeleton and as soon during the training course as the ReWalk Trainers and the participants (with their companions) feel they can achieve the skills (at a minimum of 20 sessions). However, if by 30 sessions the participants are unable to achieve these skills, they will not be sent home with the device and will be treated as a study “failure”. Participants (with their companions) will need to demonstrate the following skills according to the SOP manual:

- Transfer into and out of the exoskeleton;

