A major secondary objective of the study is to demonstrate that participants who use the exoskeleton in addition to SOC (EAW+SOC) will have at least a 1.0 kg loss in total body fat mass by the end of the four-month intervention compared to those who receive SOC only. Other secondary objectives are to demonstrate that participants in the EAW+SOC group will have greater net improvements than participants in the SOC only group in the following outcomes: 1) Global Impression of Change (participant- and companion-rated), 2) disturbed sleep as measured by the T-score of the Patient Reported Outcomes Measurement Information System (PROMIS) Sleep Disturbance, 3) self-reported methods and measures of bowel function, 4) sum T scores of the SCI Functional Index (SCI-FI) physical function short forms, 5) sum T scores of the SCI-QOL Emotional domain, 6) sum T scores of the SCI-QOL Social Participation domain, 7) lipid profile for high density lipoprotein cholesterol (HDL-c), low density lipoprotein cholesterol (LDL-c), triglycerides (TG), and total cholesterol (TC), and 8) fasting plasma glucose (FPG) and insulin (FPI) levels for calculation of Homeostasis Model of Assessment-Insulin Resistance (HOMA-IR).

B. Sample Size

Using preliminary data generated from the Exoskeletal-assisted Walking Program at the James J. Peters VA Medical Center, three separate power calculations were performed, one for each of the primary outcome measures, the MCS/VR-36 and the sum t-score of the SCI-QOL bladder, bowel and pain item banks, and one for the major secondary measure, total body fat mass. The sample

size estimates are based on the preliminary data from these three outcome measures as a proportion of participants who achieved a clinically significant change score (MCS/VR-36 and Total Body Fat Mass) or a clinically significant percent change (SCI-QOL PMH).

Sample size/power calculation for the Primary Outcome (1) MCS/VR-36: A minimally important difference for the MCS/VR-36 is 4.0. It is hypothesized that 33% of the Intervention group and 10% of the Control group will achieve a 4.0 or greater change on the MCS/VR-36 (Table 7).

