Sample size/power calculation for the Primary Outcome (2) SCI-QOL for Bladder, Bowel and Pain: An improvement of 10% in the sum T-score of the patient-reported outcomes from the combined SCI-QOL item banks for bladder management difficulties, bowel management difficulties and pain interference is clinically significant. As such, it is hypothesized that 42% of the Intervention group compared with 10% of the Control group will demonstrate a clinically significant change of 10% improvement from baseline to the end of the intervention phase on the sum T-score in the combined SCI-QOL item banks for bladder management difficulties, bowel management difficulties and pain interference. (Table 7).

Sample size/power calculation for the Major Secondary Outcome for Total Body Fat Mass: Patients with a new SCI can be expected to gain an average of 6.0 ± 8.9 kg of fat mass in the first 14 months after injury (manuscript in preparation from our Center). This gain in fat mass appears to continue throughout the duration of their life after SCI. As demonstrated in the preliminary data, an intervention that supports a 1.0 kg (2.2 lb.) loss of fat mass is a substantial amount of fat mass to lose in three months for a person with SCI. Very few interventions have demonstrated changes in body composition of this magnitude in the SCI population. It is expected that 35% of the Intervention group compared with 10% of the Control group will maintain total body fat mass loss during the home/community use phase of the intervention.

Assuming the proportion in the control group achieving a clinically meaningful change to be 10% (or 0.100) for all three outcome measures, and estimating the attrition rate at 15%, the sample sizes range from a low of 71 per group (95% power) for the SCI-QOL PMH outcome to a high of 79 per group (80% power) for the MCS/VR-36 group. As a note about Table 7, to adjust for multiple outcome measures, a significance level of 0.025 was used in the sample size calculations for the co-primaries (MCS/VR-36 and SCI-QOL) and also for the major secondary outcome measure (Total Body Fat Mass). Based on the sample size and power calculations in Table 7, the study will enroll a total sample size of 160 participants, 80 per group.

Table 7: Sample Size/Power Calculations			
Two group continuity corrected χ^2 test of equal proportions (odds ratio = 1) (equal n's)	MCS/VR-36	SCI-QOL (PMH)	Total Body Fat Mass
Test significance level, α	0.025	0.025	0.025

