group will have a clinically meaningful change in the outcome measures for sample size/power calculations. Ten percent is thought to be a conservative estimate as there is no reason to expect the control group to have clinically meaningful changes in quality of life measures or in total body fat mass while continuing to receive SOC for their spinal cord injury. However, as a means of verifying the control proportion of 10% (or 0.100), the proportion of participants considered successful in the control group for all three outcomes and 95% confidence intervals for the proportions will be reviewed upon the completion of the feasibility phase. Based on the extensive experience with this population it is highly unlikely that the assumed success rates in the control group (SOC) will be any higher than the assumed 10%.

At the completion of the feasibility phase, the study will be moved to a continuation phase where the remaining sites (9 remaining sites) will be activated and the remaining participants will be recruited.

D. Baseline Comparability

Baseline comparability between the treatment groups will be evaluated with respect to such variables as demographics (e.g., age, gender, and race) and baseline values of outcome measures (MCS/VR-36, SCI-QOL, total body fat mass, etc.). Chi-square and analysis of variance techniques, as appropriate, will be used to determine any differences in distribution of the variables across the treatment groups. Any variable that appears to be different between the groups ($p < 0.10$) will be considered as a potential covariate in statistical analyses.

E. General Outcome Analysis Guidelines

All statistical tests will be 2-sided. The two primary and major secondary outcome measures will be tested at a 0.025 level of significance. Because of the large number of secondary outcomes to be analyzed, all other secondary outcomes will be tested at a significance level of 0.01 to maintain control over Type I error. SAS 9.4 will be used to conduct all the statistical analyses. A variety of analytic methods will be used for the primary endpoints, secondary endpoints and other analyses.

F. Analysis of Primary and Major Secondary Outcome Measures

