The primary analysis will be based on an intent-to-treat (ITT) model. All participants who are randomized will be included for both groups, whether they are study completers (participants who complete the study through the four-month intervention phase) or early terminators (drop-outs). In order to test the hypotheses for the primary and major secondary outcome measures, each randomized participant will be deemed a success or failure at attaining: 1) ≥ 4.0 point improvement in the MCS of the VR-36, 2) $\geq 10\%$ improvement in the SCI-QOL bladder management difficulties, bowel management difficulties and pain interference sum T score, and

3) ≥ 1 kg. total body fat mass loss. For each of the outcomes, the proportion of participants successful at achieving a clinically significant improvement will be compared between the two groups (Intervention vs. Control) using a chi-square analysis. These will constitute the primary and major secondary efficacy analyses. Participants who drop out will be treated as failures. As such, by design, there will be no missing data: participants either meet the outcome criteria (successes), do not meet these criteria (failures) or they drop out (also failures).

G. Secondary Analyses

In addition to the primary analysis, several secondary analyses will be performed and are described below.

1. Analyses will be performed that include only those participants who complete the study (excluding drop-outs):
 - a) Chi-square analyses of the primary and major secondary outcome measures (proportion of successes) will be repeated for only those participants who complete the 4-month intervention phase.
 - b) Analyses of the MCS/VR-36, SCI-QOL, total body fat mass loss, Global Impression of Change and other secondary outcome measures will include comparisons of the mean difference scores (change from baseline to the end of the intervention phase) of these outcome variables using t-tests.

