2. Interim time points of data collection for all outcome variables have been incorporated into the study design. These time points are: baseline, after training/orientation phase, two months into the intervention phase, and then again after four months of the intervention phase (primary and major secondary outcomes main time point). Secondary analyses of the MCS/VR-36, SCI-QOL, total body fat mass loss, Global Impression of Change and other secondary outcome measures will include comparisons of the mean difference scores (change from baseline to the end of each time point) of these outcome variables using t-tests. Other secondary analyses of outcome measures will be performed that use the all data available. For these continuous variables, repeated measures analysis of covariance will be used to analyze them, with baseline scores, plus any variables determined from the baseline comparisons, being used as covariates in the analyses. SAS MIXED and GENMOD procedures, which allow for the use of incomplete data sets, will be used if it can be safely assumed that missing data are missing at random. If this assumption is not valid, a multiple imputation strategy of the missing responses will be implemented which does not rely on the assumption that missing data occur at random. This will allow an intent-to-treat approach for the statistical analyses, where complete cases are not required.

3. An analysis to determine the characterization of the drop-outs will be performed by using descriptive and correlation statistics. The reasons for drop-out and the number of sessions/time points completed will be described. A correlation analysis will be performed with the reasons for drop-out and the demographic variables and other potential variables to identify characteristics of persons who drop out of the study.

H. Monitoring of Study by Study Group and Executive Committee

The Study Group (all of the Site Investigators) and Executive Committee will meet 6 to 9 months after patient recruitment begins and at annual intervals thereafter until the end of the study. Three weeks prior to these meetings and at 6-month intervals between the meetings, these groups will be provided a report that will allow them to assess study progress. Since both groups are composed of study participants, no outcome data will be provided in these reports. The information provided will include data on:

1. Screening, enrollment and retention
2. Patient background characteristics at entry

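### Three analyses are planned for each continuous secondary outcome and none is named as the result; two are unadjusted change-score t-tests, one of them in completers only

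*Combined protocol and SAP*

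**What the plan says.** Section XIII.G plans three kinds of analysis for the continuous forms of MCS/VR-36, SCI-QOL and fat mass, and for the other secondary outcomes:

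- **Item 1(b), completers.** "Analyses will be performed that include only those participants who complete the study", with drop-outs left out. Mean change from baseline to month 4 is compared by t-test with no covariate.
- **Item 2, each time point.** Mean change to each later assessment is compared by t-test. No analysis set is stated.
- **Item 2, all available data.** "repeated measures analysis of covariance will be used to analyze them, with baseline scores" and any imbalanced baseline variables as covariates. The SAP presents this as the route to an intent-to-treat analysis, with multiple imputation if missingness at random cannot be assumed.

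Section XIII.E sets the levels: "The two primary and major secondary outcome measures will be tested at a 0.025 level of significance", and "all other secondary outcomes will be tested at a significance level of 0.01 to maintain control over Type I error". It does not say which of the three analyses faces the 0.01 threshold, or which level applies to the continuous forms of the three responder outcomes. Section XIII.I says the tables will show p-values from both the difference scores and the mixed models.

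Section XIII.F defines a completer as someone who finishes the four-month intervention phase. Under section VIII.H, "if by 30 sessions the participants are unable to achieve these skills, they will not be sent home with the device"; they are then treated as study failures. Section IX.D gives this test to the Intervention group only. Section VIII.G ends participation for anyone who loses a companion and does not train another.

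**The concern.** Two things are at stake.

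The first is which p-value counts. A level of 0.01 per outcome controls error only if one test per outcome is held to it. With three kinds of analysis and no order among them, the reported result could be chosen after the data are seen.

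The second is the quality of the comparison. Equal numbers lost per arm do not make completers comparable if the reasons for loss differ. An Intervention participant may have to pass a skills test with a companion, and keep a companion, to reach month 4 as a completer. A Control participant faces no such hurdle. If skill attainment is related to change in the outcome, the completers' contrast can be non-zero with no device effect. The t-test on change is also less precise than the ANCOVA already planned for the same data.

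**Working it through.** **1. The plan's own figures.** Table 7 uses a test described as "Two group continuity corrected" chi-square, two-sided alpha 0.025. For MCS, "33% of the Intervention group and 10% of the Control group will achieve a 4.0 or greater change on the MCS/VR-36" (0.333 against 0.100 in the table), with 80% power.

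- n′ = [z(α/2)·√(2p̄q̄) + z(β)·√(p₁q₁ + p₂q₂)]² / Δ² = [2.241 × 0.5825 + 0.842 × 0.5587]² / 0.233² ≈ 58.1
- n = (n′/4)·[1 + √(1 + 4/(n′Δ))]² ≈ 66.4, so 67

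The same method gives 60 (SCI-QOL, 0.42 against 0.10, 95% power) and 66 (fat mass, 0.35 against 0.10, 85% power). Dividing by 0.85 gives 79, 71 and 78. All match Table 7. With 80 randomized per arm, 80 × 0.85 = 68 completers per arm, as section IV.C states.

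**2. Selection in the completers' contrast, with no true effect.**

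Inputs from the plan: level 0.01 (section XIII.E), "All statistical tests will be 2-sided", 80 per arm, 68 Control completers.

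Assumptions:
- A share q of the Intervention arm is removed from the bottom of a normally distributed trait.
- That trait has correlation c with the **change score**.
- Control losses are unrelated to outcome, and the Intervention arm has no other losses.

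Formulas, in SDs of change, with t the q-quantile of the standard normal:
- m = φ(t)/(1 − q); bias b = c·m
- variance of change in the selected arm v = 1 − c²·m·(m − t)
- SE = √(v/[80(1 − q)] + 1/68)
- error rate = Φ(b/SE − 2.576) + Φ(−b/SE − 2.576)

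Example, q = 15% and c = 0.3: t = −1.036, m = 0.274, b = 0.082, v = 0.968, SE = 0.170, b/SE = 0.484, error rate 0.0193.

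| q | c = 0.1: bias, error | c = 0.2 | c = 0.3 | c = 0.5 |
|---|---|---|---|---|
| 5% | 0.011, 0.0102 | 0.022, 0.0106 | 0.033, 0.0114 | 0.054, 0.0142 |
| 10% | 0.019, 0.0105 | 0.039, 0.0120 | 0.058, 0.0147 | 0.097, 0.0241 |
| 15% | 0.027, 0.0110 | 0.055, 0.0140 | 0.082, 0.0193 | 0.137, 0.0398 |
| 20% | 0.035, 0.0115 | 0.070, 0.0164 | 0.105, 0.0253 | 0.175, 0.0616 |

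Reversing the sign of c reverses the bias but leaves the two-sided error rate the same.

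**3. Precision.** Let r be the correlation between baseline and month 4, with equal variances at both times and equal n. The variance of the arm difference is proportional to 2(1 − r) for the change score and to 1 − r² for ANCOVA. The ratio is (1 + r)/2. The detectable difference (outcome SDs, level 0.01, 80% power, 68 per arm) is (2.576 + 0.842) × √(2/68) = 0.586, multiplied by √(2(1 − r)) or √(1 − r²).

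| assumed r | ANCOVA variance / change-score variance | Detectable, t-test on change | Detectable, ANCOVA |
|---|---|---|---|
| 0.3 | 0.65 | 0.69 | 0.56 |
| 0.5 | 0.75 | 0.59 | 0.51 |
| 0.7 | 0.85 | 0.45 | 0.42 |
| 0.9 | 0.95 | 0.26 | 0.26 |

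The documents give no value for q, c or r.

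**The case against.** A reader might infer three stronger claims. The documents support none of them.

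- **That the completers t-test is the main secondary analysis because it comes first.** Section XIII.G lists several analyses and sets no order of importance among them. The all-data ANCOVA has equal standing.
- **That every Intervention completer has passed the skills test.** The protocol calls those who fail it study failures, never drop-outs, and item 1 excludes drop-outs. Table 6 shows post-intervention evaluations for both groups. If those who fail are assessed at month 4 and counted as completers, the skills filter on this set disappears. The plan does not say which holds.
- **That the bias favours the device.** This needs skill attainment to go with greater improvement. Participants with worse baseline scores have more room to improve, so the sign could be the opposite. A trait related equally to baseline and month-4 level would not shift the change score at all. Selective loss of Controls could add to or offset any bias.

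Other points also stand. The Basic Skills Test, taken by everyone before randomization, is meant to screen out likely later failures, so the filtered share may be small; at 5% the error rate is 0.010 to 0.014. Section IV.C expects no more than 15% attrition, equally split. A change score does use the baseline, only less efficiently, and the gain shrinks to 5% at r = 0.9. For the Global Impression of Change, already a rating of change, the precision argument has no clear meaning. Section II calls the secondary outcomes exploratory, and a supportive completers analysis is ordinary practice.

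What remains is that no analysis is designated and that the weaker methods stand level with the better one.

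**Conclusion.** The point holds as an open choice among three kinds of analysis, two of them inferior to the third. The completers' contrast lacks the protection of randomization because the gates that can affect completion act after randomization, in practice in one arm. The companion rule is not worded by arm, but retraining a companion matters only where a device is in use.

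Neither the size nor the direction of bias can be fixed from the documents. Under the assumed ranges (5 to 20% filtered, correlation 0.1 to 0.5 with change) the error rate at nominal 0.01 runs from essentially nominal to about 0.06. The precision loss is firmer in kind, since ANCOVA has lower variance for any r below 1 with equal variances, but its size depends on an unknown r. The error from choosing among p-values is not quantified here.

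The primary and major secondary responder tests include all randomized participants with drop-outs as failures, and are unaffected. This is a free improvement, not a threat to the main conclusions.

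**What to change.** In section XIII.G:

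1. Name the month-4 contrast from the baseline-adjusted repeated-measures model, in all randomized participants, as the single inferential analysis for each continuous secondary outcome and for continuous MCS, SCI-QOL and fat mass. State the level that applies to the last three.
2. Label the completers t-tests and the per-time-point t-tests as supportive.
3. State whether participants who fail the Advanced Skills Test count as drop-outs and whether they are assessed at month 4. Include them in the model with whatever assessments they have.

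Baseline adjustment does not by itself remove selection. Keeping all randomized participants does, subject to the missing-data assumption, so the third item matters.

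The cost is SAP wording before outcome data are unblinded. The model is already planned, and no added visits or sample size are needed.

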ISNCSCI Exam			x			x					x	
BMD Scan			x									
Bi-lateral foot x-ray			x									
CT scan, if indicated			x									
Home Evaluation			x									
Companion Evaluation		x										
OUTCOME Assessments		5 Session EAW Training										
iDXA Body Composition			x		x			x				
VR-36			x		x			x				
SCI-QOL			x		x			x				
Global Impression of Change Scale			x		x			x				
PROMIS Sleep Disturbance			x		x			x				
SCI-FI			x		x			x				
Bowel Function			x		x			x				
Blood draw (Lipids/Glu/Ins)		x		x			x					
QUALITY CONTROL Data		Randomization										
EAW Basic Skills Test			x		x			x				
Usual Activity Log			x	1 x Weekly		1 x Weekly						
Step Counter (Intervention group only)			x	Each Session		1 x Weekly		x				
EAW Mobility Tests (Intervention group only)			x	Each Session		x		x				
EAW Activity Log (Intervention group only)			x			1 x Weekly		x				
EAW Advanced Skills Test			x					x				
Home set-up		x			PRN Home Interim visits							
Exit survey							x ¹	x ¹				

Table 6. Legend	
Home and Companion Evaluations	Home and companion evaluations will be performed on all participants who have passed the medical screening criteria and will be performed prior to randomization to avoid unbalanced or biased groups.
OUTCOME Assessments	Outcome assessments will only be performed on those potential participants who have passed all screening criteria. Screening failures and reasons will be recorded on study forms.
SOC	Standard of care is defined as wheelchair use and usual lifestyle activities.
Standard of Care Review	Participants complete an interview with a study team member to review usual lifestyle activities and Usual activity weekly log.
EAW Training	Intervention group attends the exoskeletal-assisted walking training for 25±5 sessions.
EAW Advanced Skills Test	EAW Advanced Skills Test is a combined participant/user and companion test. NOTE: Participants and companions must pass the EAW Advanced Skills Test to continue to home use; those who do not are treated as "study failures".
Home set-up	Only those participants and their companions who pass the EAW Advanced Skills Test will continue on to home/community use. For these participants, a second home visit for set-up will be performed by a study team member from the Site.
Exit survey	Exit surveys may be completed with the Post Intervention Phase Evaluations for both groups or after the optional EAW in-hospital training for the control group

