Intervention Group: Training for the Intervention group will consist of 25±5 sessions of EAW training followed by an EAW Advanced Skills Test that will determine the eligibility of the participant to take the device home. Training will take place at the VA hospitals, in the CBOCs under the same FWA as the sites, or in the participant's home/community. Participants in the Intervention arm will take the device home to use. During the training and home/community use components of the study, the built-in step counter on the device will record the weekly total number of steps taken. The EAW Activity Log will be completed by each participant on a weekly basis to record the location, duration and frequency of device use. The Trainers will follow up weekly with the participants for completion of this task.

Control Group: In order to provide a similar level of attention to the Control group during the Orientation/Training phase, the Control group will receive interviews to identify types of physical activities in which they usually participate. Control participants will be instructed to complete the Usual Activity Log on a weekly basis during the Orientation/Training course and during the four-month Intervention phase. Weekly contact by the study team will be provided to the Control group during the Orientation and Intervention phases, in person, over the phone, or through secure messaging using My HealtheVet.

IX. OUTCOME MEASUREMENTS

The frequency and specific time points of each of the outcome measurements can be found in the "Training and Testing Schedules" (Table 6).

The two primary, major secondary and secondary outcomes are measured at baseline, post Orientation/Training phase, post 2-month Intervention phase, and post 4-month Intervention phase. The main comparison for the two primary and major secondary outcomes is the change in

the outcome measures from baseline to post 4-month Intervention phase.

A. Primary Outcomes

1. Mental Health Component Summary (MCS) of the Veterans Rand-36 (VR-36) for Vitality, Social Functioning, Role-Emotional, and Mental Health.
2. The sum T-score for the SCI-QOL Physical Medical Health domain (three item banks of Bladder Management Difficulties, Bowel Management Difficulties, and Pain Interference).

B. Major Secondary Outcome

1. Total body fat mass (by DXA scan) (results will be blinded)

C. Secondary Outcomes

1. Global Impression of Change Scale (Participant- and Companion-rated);

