The Site Coordinator will be responsible for administering the Global Impression of Change Scale. This scale is a self-assessment completed by the participant (and separately by the companion) with questions about feeling better from “No change (or condition has become worse); Almost the same (hardly any change at all); A little better (slightly noticeable, but has not made any real difference); Somewhat better (the improvement is small, slightly noticeable difference); Moderately better (the improvement is a noticeable change); Significantly better (a definite improvement, a real and worthwhile difference) to Extremely better (a comprehensive improvement that has made all the difference)”. Each question is scored from 1 to 7, with 1 being no change or worse and 7 being the best change in improvement. The change reported on participant’s self-assessment on the global scale will be examined with the change reported on the SCI-QOL for correlation. The companion’s impression of the participant’s global change will be used as a proxy validation of the participant’s self-assessment. Analysis of the mean change scores for both tools would help to confirm the clinical relevance of the hypothesized 10% improvement from baseline in the SCI-QOL as a clinically relevant improvement.

The Site Coordinator will be responsible for administering the bowel function surveys and will explain to each participant to select the response that best represents what is asked by the

question. These set of questions ask about the participants views about their bowel function. The Site Coordinator will ensure that each participant answers every question, by marking the answer as indicated. If the participant is unsure about how to answer a question they will be instructed to provide the best answer they can. The Site Investigator will be responsible for the history and physical examination and administering the International Standards for Neurological Classification of SCI (ISNCSCI) Examinations for level and completeness of SCI. A radiology technician or designated DXA technician at each site will perform the DXA scans. The cost of this service has been added to the budget.

G. Schedule of Observations and Laboratory Tests

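### The Global Impression of Change is already a rating of change, yet the SAP analyses it as change from a baseline rating; the follow-up rating should be compared directly.

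*Combined protocol and SAP*

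**What the plan says.** Section IX.F describes the Global Impression of Change as a seven-category self-assessment of how much better the participant is, with a separate rating by the companion: "Each question is scored from 1 to 7, with 1 being no change or worse and 7 being the best change in improvement". Section IX.C lists it first among the secondary outcomes. The opening of Section IX fixes the timing: "The two primary, major secondary and secondary outcomes are measured at baseline, post Orientation/Training phase", and then at months 2 and 4 of the Intervention phase. Table 6 lists the scale with the other outcome assessments.

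Section XIII.G names the scale twice, each time stating that "Global Impression of Change and other secondary outcome measures will include comparisons of the mean difference scores". Item 1b (completers) plans to compare "mean difference scores (change from baseline to the end of the intervention phase) of these outcome variables using t-tests". Item 2 plans "comparisons of the mean difference scores (change from baseline to the end of each time point) of these outcome variables using t-tests", again naming the scale. Item 2 then adds a repeated measures analysis of covariance for continuous variables, "with baseline scores, plus any variables determined from the baseline comparisons, being used as covariates in the analyses".

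Section IX.F also plans to correlate the change reported on this scale with the change on the SCI-QOL. It expects mean change scores on both tools to help confirm that a 10% SCI-QOL improvement is clinically relevant.

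**The concern.** A rating of change needs a reference point. At follow-up this is understood to be the start of the study. At baseline there is none: under Section III.A the baseline evaluations come before device fitting, the five basic training sessions and randomization. No section says what period a baseline rating should cover. It is therefore either a uniform 1 or an answer to an undefined question, and the SAP subtracts it from the follow-up rating.

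At stake are the meaning of the result on this secondary outcome and, usually, some of its precision. The same ambiguity touches the supporting comparison with the SCI-QOL in Section IX.F.

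**Working it through.** The plan states no effect size, SD or power for this outcome, so there is no figure to reproduce. The check has two parts.

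**Interpretability.** Take the seven categories in order.
- Baseline 4, month 4 rating 3: difference 3 − 4 = −1. This participant reports some improvement at month 4 but is scored as having worsened.
- Baseline 3, month 4 rating 5: difference +2. Baseline 1, month 4 rating 3: difference +2. These two participants report different amounts of improvement at month 4 but receive the same score.
- Category 1 pools no change with deterioration, so equal differences need not mean equal change.

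**Precision.** Let Y be the follow-up rating and B the baseline rating, k = SD(B)/SD(Y), and r their correlation. Then

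Var(Y − B) / Var(Y) = 1 + k² − 2rk.

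This equals 1 when r = k/2, so subtraction costs precision when r is below k/2 and gains it when r is above. If every B is 1, then k = 0, the constant cancels between arms and the t-test is unchanged.

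Inputs for the effect on power:
- Completers per group: 80 × 0.85 = 68 (IV.C).
- Two-sided test at 0.01 (XIII.E).
- Assumed: a true difference that gives 80% power on the direct rating, (2.576 + 0.842) × √(2/68) = 0.586 follow-up SDs.
- Assumed, because the documents give no values: k of 0, 0.5 or 1, and r from 0 to 0.7.

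| k | r | Variance ratio | Power on the difference score |
|---|---|---|---|
| 0 | any | 1.00 | 80% |
| 0.5 | 0 | 1 + 0.25 = 1.25 | 68.5% |
| 0.5 | 0.3 | 1 + 0.25 − 0.30 = 0.95 | 82.4% |
| 0.5 | 0.7 | 1 + 0.25 − 0.70 = 0.55 | 97.9% |
| 1 | 0 | 1 + 1 = 2.00 | 43.7% |
| 1 | 0.3 | 1 + 1 − 0.60 = 1.40 | 62.3% |
| 1 | 0.5 | 1 + 1 − 1.00 = 1.00 | 80% |
| 1 | 0.7 | 1 + 1 − 1.40 = 0.60 | 96.7% |

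Break-even is r = 0.25 at k = 0.5 and r = 0.5 at k = 1.

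**The case against.** The best defence is that the list in XIII.G is loose. It also contains fat mass loss, which is already a change and which nobody would difference again. On that reading the rating itself serves as the change score. This is possible, but it does not settle the matter: both items define the difference scores explicitly as change from baseline, and the protocol collects a baseline rating that could be subtracted. A programmer following the text would subtract it.

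Other objections stand and limit the point.
- A reader might infer that the subtraction can only add noise. The documents do not support that. With the scale's floor at no change or worse, a uniform baseline of 1 is quite plausible and harmless, and a strong shared response style (r above k/2) would reduce the variance.
- A reader might infer that the analysis of covariance is equally damaged. It is not. It estimates the baseline coefficient rather than fixing it at 1, so an uninformative baseline costs about one degree of freedom. If it is applied to this scale, it amounts to a between-arm comparison of follow-up ratings. Item 2 limits it to continuous variables, and whether a seven-category rating counts is not stated.
- A reader might infer that the primary SCI-QOL threshold is undermined. The 10% criterion is fixed in advance (II.D, XIII.A, XIII.F), and no success or failure call uses the Global Impression. The correlation sentence in IX.F can also be read as using the rating itself.

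**Conclusion.** The difference-score analysis of the Global Impression of Change is wrong as written, with low severity. That the difference is not interpretable follows from the documents' own definition and schedule and needs no numerical assumption, except in the harmless case where every baseline rating is 1.

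The loss of precision is conditional. At zero correlation the variance rises by 25% to 100% for k between 0.5 and 1, and nominal 80% power falls to between 68.5% and 43.7%. At a high enough correlation the loss becomes a gain. That a loss is the usual result is a judgement: without a reference point, there is little reason to expect a baseline rating to track the follow-up rating closely.

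Randomization keeps the comparison between arms free of bias from this source. Section II calls the secondary outcomes exploratory and does not use them for power, so the primary analyses, the major secondary analysis and the sample size are unaffected.

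**What to change.** In XIII.G items 1b and 2, take the Global Impression of Change out of the change-from-baseline list. State that the participant and companion ratings are each compared between arms as reported, at post-training, month 2 and month 4, and that the baseline rating is neither subtracted nor used as a covariate. A t-test is acceptable; a rank or ordinal method is optional.

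In IX.F, state that SCI-QOL change is examined against the month-4 rating itself.

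The cost is SAP and protocol wording. No new data are needed, and the 0.01 level and the sample size stay as they are. Removing the baseline form would achieve little now: Table 5 ends enrollment in FY20 and this version is dated July 2021. Baseline ratings already collected can simply be left out of the comparison.
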